6. RESEARCH QUESTION AND OBJECTIVES

Primary Objectives

- To assess demographic and clinical characteristics of NVAF patients treated with oral anticoagulants (OACs) in Colombia.
- To describe treatment patterns (eg. OAC usage, dose, concomitant medications, persistence)

Exploratory Objectives

- To descriptively assess the time to clinical events (Effectiveness and Safety Outcomes) among patients persistent on OAC therapy.

Effectiveness outcomes: First Stroke/ Systemic Embolism; CCI

Safety outcomes: Major bleeding, CCI

[figure not shown]

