7. RESEARCH METHODS

7.1. Study Design

Observational, descriptive study of a retrospective cohort of adult patients diagnosed with NVAF in selected Health Maintenance Organization (HMO) of Colombia. These patients will be identified from the drug claim database, whose index date of the study will be the first prescription with any of the oral anticoagulants, that is, they are patients with NVAF for the first time starting a therapy with any of the NOACs between January 1, 2013 and June 30, 2018 and follow up period will be among January 2013 to July 2019, to ensure that the last patients can provide follow-up for one year. Patients will be required to have an NVAF diagnosis before or on the index date and health plan for 6 months pre-index date (baseline period).

Following, it will be verified that the patients meet the inclusion and exclusion criteria of the study. Once patients are selected and with the index date of each patient, they will be followed-up until discontinuation, switch of treatment, death or first event of stroke/ systemic embolism, major bleeding event, death or end of follow-up. Patients who are lost to follow-up, change of HMO and do not have access to the medical record will be considered as missing (Figure 1).

Figure 1. Study Design

[figure not shown]
The information will be analyzed in two moments: (i) the period of the index date, where the baseline information of patients will be collected; (ii) and the follow-up period, during this period the clinical results will be evaluated as well as the continuation of the treatment in the study population and for specific subpopulations.

Those patients who initiated treatment with any oral anticoagulant between January 2013 and June 30, 2018 will be included. This means that patients who start warfarin and NOACs would

be included within this period. Patients who initiate NOACs within the established period and who have been exposed to warfarin before 2013 will also be included.

Only the exposure period will be considered with the initial treatment, even in those patients who were on warfarin treatment before 2013, in the latter, the follow-up will be the treatment initiation with a NOAC in case of change after 2013. Follow-up will be carried out until the patient has a switch of treatment, discontinuation, death, first stroke/ systemic embolism, or major bleeding, or until end of follow-up, June 30, 2019 (Figure 2).

Figure 2. Inclusion of Patients

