7.2. Setting

The study will be conducted with the Audifarma patient cohort that meets the inclusion and exclusion criteria between the periods from January 2013 to June 30, 2018. The follow up period will be among January 2013 to July 2019, to ensure that the last patients can provide follow-up for one year.

This study will include the entire population in which medical records can be accessed. This will depend on the authorization of the HMOs for review of medical records. Participating patients will be followed-up until the patient has a stroke/systemic embolism, major bleeding, discontinuation, change of treatment or until the data collection period is completed.

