7.2.2. Exclusion Criteria

Patients meeting any of the following criteria will not be included in the study:

- e) Patients with any of the following diagnoses prior to the use of the treatments of interest or index date:
 - Valvular heart disease or valve replacement – ICD-10 codes: I05, I06, I07, I08, I09, I22, I34, I35, I36, I37, I38, I39, I700, I702-I709; Q22, Q23, Q25, T82,Z95.
 - Pregnancy during the study period. ICD-10 O00-O9A
 - Diagnosis of venous thromboembolism (VTE) – ICD-10 codes: I26, I80 - I82;
- f) Individuals with a transitory diagnosis of NVAF prior to the use of the treatments of interest or index date;
- g) Exposure to more than one OAC on or after the index date, during the follow-up period.
- h) NOAC doses different from those recommended by the manufacturing laboratories.

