Persistence	Clinical outcome	Claim databases	Yes, No
OAC treatment	Treatment	Claim databases	Warfarin, apixaban, rivaroxaban, dabigatran
Diagnosis at index date	Treatment	Claim databases	Diagnosis AF based on ICD-10
Date of OAC prescription	Treatment	Claim databases	Date reported dd/mm/yy
Dosage of the initial OAC treatment	Treatment	Claim databases	Mg per dose
Initial frequency of OAC treatment	Treatment	Claim databases	Number of doses at initial OAC treatment
OAC escalation	Treatment	Claim databases	Yes, No
Type of OAC escalation	Treatment	Claim databases	Dose increase or dose decrease
Time to OAC escalation	Treatment	Claim databases	Date reported dd/mm/yy
CCI			

Variable	Role	Data source (s)	Operational definition
CCI			
INR testing monthly in patients with warfarin	Treatment	Medical record	INR reported in the medical record per month
Switch to another OAC treatment:	Treatment	Claim databases	Yes, No
Time to Switch to another OAC treatment	Treatment	Claim databases	Date reported dd/mm/yy
Causa de cambio	Treatment	Medical record	Adverse events, effectiveness, adherence, patient preference, administrative problems, not reported, others
Concomitant therapies by OAC prescription	Treatment	Medical record	NSAIDs, Angiotensin-converting-enzyme (ACE) inhibitors, Amiodarone, Beta-blockers, Angiotensin II receptor blockers (ARBs), Aspirin, Clopidogrel, Digoxin, Diuretics, calcium blockers, statins, proton pump inhibitor, selective H2 antagonists, antidiabetics, insulin, serotonin reuptake inhibitors
Previously exposed to warfarin	Treatment	Claim databases	Yes, No

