7.3.1. Definition of outcome variables

- **OAC escalation:** The dose escalation of the OAC dose will be considered as a dose frequency according to the index dose, as well as the follow-up doses. The proportion of patients experiencing "dose increase", "dose decrease" or "no change" during follow-up with respect to the index dose will be measured, and the time to dose increase or decrease will be calculated.

C
C
I

C
C
I

- **Switch of treatment:** A switch among anticoagulants will be defined as a prescription filled for non-index anticoagulants within +/- 30 days after the date of discontinuation.
- **Persistence:** Persistence will be defined as the time under OAC therapy, calculated as the time in days from the index date to the date of discontinuation or change to treatment. As previously stated, discontinuation will be defined as a change of treatment, that is, to another OAC, or when there is no evidence of a prescription for 60 days from the last supply delivered, whichever comes first.

Therefore, if a patient does not receive his next prescription for the OAC therapy within 60 days after the end of the previous prescription, it will be considered that he discontinued therapy, and the date of the last prescription will be considered as the final date of persistence.

Persistence with OAC therapy will be considered during the period of individual patient follow-up. Patients will be censored at the end of their follow-up period.

- **Major bleeding:** Patients presenting any of the following diagnoses during the follow-up period:

ICD-10	Description
I60	Subarachnoid haemorrhage
I61	Intracerebral haemorrhage
I62	Other nontraumatic intracranial haemorrhage
I690	Sequelae of subarachnoid haemorrhage
I691	Sequelae of intracerebral haemorrhage
I692	Sequelae of other nontraumatic intracranial haemorrhage
S064	Epidural haemorrhage
S065	Traumatic subdural haemorrhage
S066	Traumatic subarachnoid haemorrhage
I850	Oesophageal varices with bleeding
K250	Acute with haemorrhage

Apixaban

B0661148- NON-INTERVENTIONAL STUDY PROTOCOL

Final, 10 October 2019

ICD-10	Description
K252	Acute with both haemorrhage and perforation
K254	Chronic or unspecified with haemorrhage
K256	Chronic or unspecified with both haemorrhage and perforation
K260	Acute with haemorrhage
K262	Acute with both haemorrhage and perforation
K264	Chronic or unspecified with haemorrhage
K266	Chronic or unspecified with both haemorrhage and perforation
K270	Acute with haemorrhage

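### Exclusion (g), as written, removes everyone who starts a second OAC after index, yet the plan needs those patients as endpoints and censoring events

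*Combined protocol and SAP*

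**What the plan says.** Section 7.2.2 lists, among criteria that keep a patient out of the study, "Exposure to more than one OAC on or after the index date, during the follow-up period". The abstract (Section 2) carries the same criterion. Section 7.6.4 has the inclusion and exclusion criteria verified before data are collected, so (g) acts before chart abstraction.

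Other sections treat a patient who changes OAC as a cohort member:

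- Section 7.1: "Follow-up will be carried out until the patient has a switch of treatment, discontinuation, death, first stroke/ systemic embolism, or major bleeding".
- Section 7.2: "Participating patients will be followed-up until the patient has a stroke/systemic embolism, major bleeding, discontinuation, change of treatment".
- Section 7.3, Table 1 collects switch (Yes/No), "Time to Switch to another OAC treatment" and the cause of the change.
- Section 7.3.1, under Persistence: "discontinuation will be defined as a change of treatment, that is, to another OAC", or a 60-day gap in supply, whichever is earlier.
- Section 7.7 makes change of treatment a censoring reason for the clinical outcomes and plans a time-to-event analysis of it. The abstract plans the same analysis.

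The second primary objective in Section 6 is "To describe treatment patterns (eg. OAC usage, dose, concomitant medications, persistence", so it names persistence.

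Two passages bear on what follow-up means in (g). Section 7.1 says "Only the exposure period will be considered with the initial treatment", which points to time on the first OAC. Section 7.2 says "The follow up period will be among January 2013 to July 2019", which is a calendar window.

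**The concern.** Criterion (g) selects the cohort on something that happens after the index date. At index nobody knows who will later receive a second OAC. Excluding those who do keeps only patients whose later course met a condition, and that condition is part of an outcome being measured.

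Three things are at stake. The switch outcomes (proportion, time, cause) would be empty by construction. Persistence, which belongs to a primary objective, would be estimated after one of its two failure types had been deleted from the cohort. And because a narrower reading is possible but not stated, cohort membership would depend on who programs the selection.

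**Working it through.** **1. The passages side by side.** The plan gives no switch rate or persistence figure to reproduce, so the first check is logical. Suppose (g) is applied to the whole follow-up period. No retained patient can then have a second OAC. The switch variable is always No, time to switch has no events, cause of change is never abstracted, nobody is censored for change of treatment, and the switch part of the discontinuation definition never applies. No visible passage limits (g) to concurrent use or to the index day, or says that it means censoring.

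**2. Direction for Yes/No persistence.** Let s be the share of patients whose follow-up ends in a switch and d the share ending in other discontinuation. Persistence is 1−s−d with switchers kept and (1−s−d)/(1−s) with them removed. The second is larger whenever s > 0 and some patients persist. This needs no assumed rate.

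**3. Size, under assumed rates.** From the plan: index dates January 1, 2013 to June 30, 2018 and end of follow-up June 30, 2019, hence 1 to 6.5 years of potential follow-up, taken as uniform. Assumed hazards per year: discontinuation d = 0.30, stroke or bleed e = 0.05, switch s = 0.05 or 0.10. Death is not modelled separately.

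Let G(t) be the probability of still being in follow-up at t, and M its integral (mean follow-up). Then:

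- Removed share PS = s × M; other discontinuation PD = d × M.
- Yes/No persistence = 1−PS−PD before removal and (1−PS−PD)/(1−PS) after.
- Time-based persistence = exp[−(d+s)t] before removal. After removal it is exp of minus the integral to t of d·G(u)/[G(u) − R(u)], where R(u) is the probability of being in follow-up at u and switching later.
- 3-year switch incidence = s/(s+d+e) × (1 − exp[−3(s+d+e)]).

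For s = 0.05, M = 1.823 years. PS = 0.05 × 1.823 = 9.1% and PD = 0.30 × 1.823 = 54.7%. Yes/No persistence is 100 − 9.1 − 54.7 = 36.2%, and after removal 36.2/90.9 = 39.8%.

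| Quantity | s = 0.05 | s = 0.10 |
|---|---|---|
| Patients removed | 9.1% | 17.0% |
| Yes/No persistence | 36.2% → 39.8% | 32.1% → 38.6% |
| 1-year persistence | 70.5% → 72.1% | 67.0% → 70.1% |
| 3-year persistence | 35.0% → 37.9% | 30.1% → 35.3% |
| 3-year switch incidence | 8.7% → 0% | 16.5% → 0% |

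Over d = 0.20 to 0.50 and s = 0.03 to 0.20, Yes/No persistence rises by 1.1 to 16.5 points and 1-year persistence by 0.5 to 7.7 points.

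**4. Timing can reverse the time-based result.** With late switching (0.03 in year 1, then 0.10; discontinuation 0.40, then 0.15), 1-year persistence falls from 65.1% to 62.5%. In the same scenario 3-year persistence rises from 39.5% to 43.9% and Yes/No from 39.5% to 45.4%. With early switching (0.10, then 0.03; discontinuation 0.30), 1-year persistence rises from 67.0% to 72.2%.

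**5. Calendar-window reading.** Patients who start another OAC after discontinuation or an event are then removed too. At an assumed later-start rate of 0.05, 0.10 or 0.20 per year, total removal is 16.8%, 23.3% or 33.4% (s = 0.05) and 24.3%, 30.4% or 39.9% (s = 0.10).

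**6. Clinical outcomes.** Removing switchers deletes event-free time but no events. Assume 3 events per 100 patient-years, 30% yearly discontinuation and 5% to 20% yearly switching. The observed rate is then the true rate times 1.02 to 1.11 over one year, or 1.06 to 1.31 over three.

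**The case against.** The best defence is the narrower reading. Section 7.1 ends each patient's follow-up at a switch and counts only exposure to the initial treatment. If follow-up in (g) means that individual period, a drug started after index therapy ends falls outside it, switchers stay in as endpoints, and none of the bias above arises. The rest of the plan fits this better than literal removal. The point stands as a possible reading, but it is not watertight. Sections 7.1 and 7.2 also give follow-up as calendar dates, and the switch definition in Section 7.3.1 accepts a non-index fill up to 30 days either side of the discontinuation date, so a second OAC can fall inside follow-up even on this reading.

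Parts of Sections 7.3, 7.3.1 and 7.7 are redacted and Figure 2 is not shown, so the statement that nothing limits (g) covers visible text only. This matters most for the switch definition, since some of the discontinuation wording may be hidden. It does not change (g), which is fully visible in two places.

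The figures are illustrations. The Yes/No calculation counts patients whose follow-up ended in a stroke or bleed as persistent, whereas the planned time-to-change analysis is restricted to patients without those events. With that restriction and s = 0.05, the share ending in an event is 0.05 × 1.823 = 9.1%. Yes/No persistence is then (36.2 − 9.1)/90.9 = 29.8% before removal and (36.2 − 9.1)/(100 − 9.1 − 9.1) = 33.1% after. The level is lower and the shift is similar.

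Finally, the study is descriptive, makes no treatment comparison, and does not name switching in a primary objective. That is true, but persistence is named there and its definition contains the switch.

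**Conclusion.** The concern holds. As written, (g) contradicts the sections that keep switchers in the cohort, and following it literally produces zero switches and overstated Yes/No persistence. Those two results follow from the text. Their size rests on assumed rates: in the two central scenarios 9.1% or 17.0% of patients are lost and Yes/No persistence rises by 3.6 or 6.5 points. The direction for time-based persistence depends on when switching occurs: upward if it is constant or early, possibly downward at intermediate times if it is mostly late. On the narrower reading there is no bias, but the text does not settle which reading applies. Cohort membership and a primary-objective measure depend on the answer, so it must be fixed before the cohort is extracted.

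**What to change.** - Reword (g) in the abstract and Section 7.2.2 so that it applies only to patients dispensed more than one OAC on the index date.
- Keep patients who later fill a different OAC. Count the first such fill as the endpoint for persistence and switching, and censor there for stroke/systemic embolism and major bleeding. State that this applies whether or not the fill overlaps the index supply. The visible text does not address overlap, so this is an added analysis definition.
- In Section 7.3.1, reconcile the 30-day window around discontinuation with the rule that a change of OAC is itself the discontinuation.
- Say in (g) and Section 7.2 whether follow-up means the individual on-treatment period or the calendar window.
- Section 7.5 says the 7,500 patients were verified against the inclusion criteria and does not mention exclusions. State whether switchers have already been removed from that count.

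The cost is a rewording in three places plus chart abstraction for any switchers brought back. Their switch is already recorded in the claims database. If the narrower reading was always intended, the change only writes it down.

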7.2.3. Cohorts

After applying the inclusion and exclusion criteria, eligible patients will be assigned to the following four cohorts based on the OAC received on the index date.

1. Apixaban

2. Dabigatran

3. Rivaroxaban

4. Warfarin

Depending on the dosage of the NOAC prescribed on the index date, and in comparison to the standard conventions of total daily doses, patients may be classified into 3 different groups:

- **High doses:** apixaban 10 mg/day - rivaroxaban: 20 mg/day - dabigatran: 300 mg/day;
- **Low doses:** apixaban 5 mg/day - rivaroxaban: 15 mg/day - dabigatran: 220 mg/day
- **Other doses:** to be excluded, doses not recommended by the manufacturing laboratories.

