5. RATIONALE AND BACKGROUND

Non-valvular atrial fibrillation (NVAF) is an acute or chronic heart disorder that is associated with an increase in the mortality rate, strokes and other thromboembolic events (1). This is further increased by individual conditions of patients, such as hypertension, abnormal renal or hepatic function, stroke, history of or predisposition to bleeding, people over 65, among others. (2)

One of the standard treatments for management of these patients is usually vitamin K antagonists (VKA, for example, warfarin); in the analysis of net clinical benefits of this therapy it is suggested that the effect of VKA is even more positive in patients with a high score on the HAS-BLED (hypertension, abnormal renal/liver function, stroke, bleeding history or predisposition, labile International Normalized Ratio, elderly, drugs/alcohol concomitantly) scale. (3) Another therapeutic alternative is the new oral anticoagulants (NOAC) — dabigatran, rivaroxaban and apixaban —, which according to evidence have advantages in efficacy and safety compared to warfarin (4) and even when the risk of bleeding and stroke are high, the net clinical benefit appears to be greater when compared to warfarin. (5) Likewise, there is a lower prevalence of intracranial hemorrhage and its different subtypes of patients being treated with new oral anticoagulants when compared to warfarin. (6)

While it is true there are several studies that seek to understand the characteristics of patients who were diagnosed with NVAF under different treatment options, and even subpopulation analyses, the evidence at the national level is limited, both in demographic and clinical characteristics and in treatment patterns of this population. In a retrospective descriptive study of an emergency department in a third level care center in the city of Bogota, it was observed that the main comorbidities of patients with atrial fibrillation (AF) were arterial hypertension and heart failure where most patients do not receive anticoagulation. (7) In turn, for the overall population it is estimated that the prevalence of AF in Colombia (4.8%) seems to be higher than that reported in developed countries (0.03% to 1.25%) (8), according to a study conducted in a university hospital in the country (9).

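### NOAC starters on unlisted index doses are removed, so the dose description under a primary objective covers listed doses only, and no available text commits to reporting the share removed

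*Combined protocol and SAP*

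**What the plan says.** Section 6 gives as a primary objective "To describe treatment patterns (eg. OAC usage, dose, concomitant medications, persistence". The objective is not limited to particular doses. Section 5 justifies the study on the ground that "the evidence at the national level is limited, both in demographic and clinical characteristics and in treatment patterns of this population".

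Among the exclusions in Section 7.2.2, criterion h reads "NOAC doses different from those recommended by the manufacturing laboratories". Section 7.2.3 applies the criteria first and forms the four drug cohorts afterwards. It then says that NOAC patients may be grouped by total daily dose on the index date: high (apixaban 10, rivaroxaban 20, dabigatran 300 mg/day), low (apixaban 5, rivaroxaban 15, dabigatran 220 mg/day), and a third group, other doses, described as "to be excluded, doses not recommended by the manufacturing laboratories". No warfarin doses are listed, and criterion h names NOACs only.

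Table 1 in Section 7.3 takes "Dosage of the initial OAC treatment" and the initial dosing frequency from the claims database. Section 7.4.1 assigns treatment patterns to the same source, and Section 7.6.3 has patients identified there first. Section 7.7 plans frequencies and percentages for categorical variables and states that treatments will not be compared.

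**The concern.** Most exclusions, such as prior venous thromboembolism, define whom the study is about. This one selects on a variable that the study sets out to describe. Once it is applied, every NOAC patient in the cohort is on one of two listed daily doses for the drug, and the share on other doses is zero whatever happened in practice. How NOACs are dosed at initiation is a question the primary objective invites, and the cohort can answer it only in part.

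The restriction falls on the three NOAC cohorts and not on warfarin. A reader who sees high and low percentages adding to 100% for a drug would need to know how many starters were set aside to reach that total. The available text does not commit to saying so. What is at stake is the scope of a description; with no treatment comparison planned, no effect estimate is affected.

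**Working it through.** **Inputs**

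- Listed doses, the order of steps and the index-date timing: Section 7.2.3.
- Study size of 7,500: Section 7.5. It is a count of patients checked against the inclusion criteria, with no power or precision target, so there is no plan figure to reproduce for this point.
- q, the share of NOAC starters on an unlisted index dose among those who pass every other criterion: not in the documents. Assumed 2% to 20%.
- f, the NOAC share of the 7,500: not in the documents. Assumed 30% to 70%.

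**Step 1: what the cohort can show.** Criteria come before cohort assignment, and h removes the third dose group. The observed share on other doses is 0% by construction.

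**Step 2: whether another section supplies the share.** Sections 7.5 (size), 7.6.3 (identification), 7.6.4 (collection), 7.7 (analysis), 7.7.1 (missing data), 7.8 (quality control) and 7.9 (limitations) contain no count by exclusion reason, no attrition table and no caveat on this restriction. Section 7.1 cites "Figure 2. Inclusion of Patients", which is not reproduced in the available text, so a tally there is possible.

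**Step 3: whether the 7,500 helps.** It is tied to the inclusion criteria only. If it precedes the exclusions, 7,500 minus the final number gives all exclusions together, not those due to dose. For scale, the number removed for dose is 7,500 × f × q if 7,500 precedes the dose exclusion, and 7,500 × f × q/(1 − q) if it follows it. The lowest corner is 7,500 × 0.30 × 0.02 = 45; the highest is 7,500 × 0.70 × 0.20/0.80, about 1,312. This range reflects the assumptions and is not an estimate.

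**Step 4: effect on a reported share.** Let p be a share reported among listed-dose starters. With the other-dose patients put back, it becomes p × (1 − q), so the reported share is larger by the factor 1/(1 − q).

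| Assumed q | 1/(1 − q) | Reported 50% becomes | Reported 80% becomes |
|---|---|---|---|
| 2% | 1.020 | 49.0% | 78.4% |
| 5% | 1.053 | 47.5% | 76.0% |
| 10% | 1.111 | 45.0% | 72.0% |
| 20% | 1.250 | 40.0% | 64.0% |

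The difference in points is p × q. It reaches 1 point at q = 1/50 = 2.0% for a reported 50% and at 1/80 = 1.25% for a reported 80%. It reaches 5 points at 5/50 = 10% and 5/80 = 6.25%. The high-to-low ratio within a drug does not change, because both shares are multiplied by the same (1 − q).

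**Step 5: whether a count would be informative.** With an assumed 500 NOAC starters, the Wilson 95% interval is 1.1% to 3.6% for 10/500 and 7.7% to 12.9% for 50/500. A simple count would separate a negligible q from one that matters.

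**The case against.** The strongest reply is that this is an open scope choice. The exclusion appears in the abstract, in Section 7.2.2 and in Section 7.2.3. The objective names dose as one example of a treatment pattern and does not promise the share of NOAC starters on unlisted doses. Even the high/low grouping is optional, and Section 7.7 names no specific dose table. All of this stands, and percentages reported for listed-dose starters would be correct for that group.

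It can also be said that no information is lost: patients on other doses must be recognised from claims in order to be removed, so the count is a by-product of applying h. That stands too. What is missing is a commitment to report it, and silence in a protocol does not show that the report will omit it. A count by drug and a sentence on limitations would meet the bare reporting gap. The third dose category goes a little further, using data already read, because it lets the study address dose within its own objective.

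Three stronger readings are tempting and are not supported:

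- A reader might infer that the reported shares are materially wrong. Nothing in the documents puts q above 2%, and below about that level the effect is negligible.
- A reader might infer that knowing q would convert the cohort's shares to all NOAC starters. It would not. Criterion g removes anyone exposed to more than one OAC during follow-up, the diagnosis exclusions select further, and Section 7.2 adds that "This study will include the entire population in which medical records can be accessed".
- A reader might infer that dose changes after the index date are certainly still described through the OAC escalation variable in Section 7.3.1. That holds only if h applies at the index date. Section 7.2.3 points that way, but h itself carries no time limit.

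**Conclusion.** The point holds as a limit on what the dose description can show. Criterion h, read with Section 7.2.3, truncates the NOAC dose variable that a primary objective sets out to describe, and no available text plans to report the truncated part or lists it as a limitation. Warfarin dose is unaffected.

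The size is unknown. Under assumed q from 2% to 10%, a reported 80% would be 78.4% down to 72.0% among starters passing the other criteria; under smaller q the issue is trivial. The limited national evidence cited in Section 5 gives no basis for presuming either. The conclusion rests on reading the two listed daily doses per drug as the recommended set to which h refers, on reading h at the index date, and on Figure 2 not containing the count. It is a modest point about scope and reporting that is worth settling before analysis.

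**What to change.** For the dose description only, tabulate index-date total daily dose by NOAC from claims, with other doses kept as a third category (number and percentage by drug), among starters who meet the other claims-verifiable criteria. State beside the table that this denominator is still conditioned on criterion g and the other exclusions, so it is neither all NOAC starters nor the chart-abstracted cohort. State in Section 7.2.2 that h refers to the index dose. Keep the exclusion for the chart-based and exploratory time-to-event analyses, and add one sentence on the restriction to Section 7.9.

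The cost is one claims table, one clarifying phrase and one sentence. Dose and frequency are already claims variables and have to be read to apply h, so no new chart abstraction is needed. The downside is a second denominator that is not directly comparable with the cohort: criteria that may need charts, such as "Individuals with a transitory diagnosis of NVAF prior to the use of the treatments of interest or index date", or access to the record, may not be applied to it.
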